9.6. Suspension/Early Termination of the Study

The Sponsor, PI, EC, or regulatory authority may suspend or terminate the study prematurely for various significant and documented reasons. Reasons for suspension or termination may include but are not limited to insufficient subject recruitment, updated risk profile impacting subject safety, alterations in accepted clinical practice impacting study procedures, early evidence of benefit or harm of the research product, or serious or repeated deviations by the investigator.

Suspension or termination can occur at individual sites or across the study, as applicable. The decision to suspend or terminate the study should be shared in writing with all parties described above.

If the reason for study suspension is resolved, the deciding party shall inform all appropriate parties of the decision and actions to resume study procedures.

10. STATISTICAL METHODS

10.1. Statistical Hypothesis

Non-inferiority of [REDACTED] with respect to Corometrics 259cx will be tested using the following primary hypothesis:

Reliability as measured by Success rate (SR) for FHR data:

$$H_0 = \text{Mean SR } [REDACTED] - \text{Mean SR (Corometrics 259cx US)} \leq -10\%$$

$$H_A = \text{Mean SR } [REDACTED] - \text{Mean SR (Corometrics 259cx US)} > -10\%$$

The test will be performed using two-sided 95% CI of the difference in Mean SR. If lower 95% CI of the difference is greater than -10%, non-inferiority will be concluded.

10.2. Sample Size Determination

Minimum sample sizes are described in Section 4.7.

The sample size has not been derived from a statistically powered endpoint but has been determined based on a review of the literature, bench testing results and publicly available regulatory filings.

Based on those factors it has been concluded that 30 Corometrics and Lotus data sets would sufficiently confirm the intended use of the investigational maternal fetal monitor.

10.3. Statistical Analysis

Data collected will be analyzed by the GEHC Statistician and Engineering Team.

10.3.1. General Statistical Methods

The study data will be presented in tables, listings, and figures. Data will be summarized using descriptive statistics. The descriptive statistics for continuous variables will include mean, standard deviation, median, Q1 and Q3, minimum, maximum, and sample size. Categorical variables will be described with counts, percentages, and sample size. A 95% confidence interval may be presented, when necessary. For comparison (between arms or against null values), categorical variables will be tested using appropriate contingency table analyses (exact or chi-square

Study Title: Maternal Fetal Device Performance Testing During Antepartum Singleton Monitoring

Study Number: SA-000072

Version Number: 2.0

Version Date: 23SEP2024

GE HealthCare

approximations), and continuous variables will be tested using Student's t-test or non-parametric methods, depending on variable distribution. P-values will be presented to three decimal places and p-values less than 0.001 will be presented as '<0.001'.

To determine whether the FHR data [REDACTED] Doppler US is non-inferior to Doppler US from the Corometrics 259cx in terms of reliability, the data collected from the two devices will be compared. Data is generated at a rate of 4 samples per second.

All the processing and statistical analysis will be done by the CSV assessed software application (CoroCare Process Software) or SAS v9.4. Using the CoroCare process software, the collected data will be stored in a CSV file which has a specific column allotted to each parameter.

10.3.2. Analysis of Primary Endpoint(s)

Fetal Heart Rate (FHR)

For each subject, the whole length of time when both Corometrics 259cx and [REDACTED] independently record data will be considered for statistical analysis. The reliability of the FHR data will be analyzed based on the following primary endpoint.

Success rate (SR) for FHR data:

To ensure that most of the epochs are available and evaluable, the individual SR, which measures the percentage of time that [REDACTED] or Corometrics Ultrasound (independently) generates a value for FHR, will be computed per subject (irrespective of the other device generating a value or not)). Overall SR across subjects will be summarized along with its 95% CI for each device.

$$SR(FHR)_i(\%) = \frac{a_i}{a_i + b_i} * 100$$

Where,

SR_i is the ith individual SR;

a_i is represents the number of sample points when the FHR is present (i.e. has a value other than 0) for the ith subject;

b_i is the number of sample points when the FHR is not present (i.e. the device is turned on but has a value of 0) for the ith subject;

From the start of the FHR trace, only a segment of 30 minutes duration will be considered for calculating the SR value. If the data length is greater than 30 minutes, the first 30 minutes of data will be considered for analysis. If either Corometrics or [REDACTED] has less than 30 minutes of recording, the data from both devices will be eliminated from the primary endpoint analysis but could be used for engineering development. Any gaps in the data due to pausing study procedures will be excluded from the 30-minute monitoring data that will be used for analysis. The difference in mean SR (Lotus – Corometrics 259cx) will be computed along with its two-sided 95% CI to test non-inferiority. If the lower 95% CI is greater than -10%, non-inferiority will be concluded.

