3.2. Study Endpoints

3.2.1. Primary Endpoints

The primary endpoint of this study is collection of FHR data from 30 subjects undergoing routine monitoring during antenatal period to allow for analysis of the reliability of the two maternal fetal monitors.

Reliability will be measured in terms of success rate which is defined as percentage of time in which the device gives FHR reading during the study monitoring period. Non-inferiority of [REDACTED] with respect to Corometrics 259cx will be tested using a non-inferiority margin of -10%.

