4.3. Number of Subjects/Cases

The study includes a minimum of 30 subjects (with a maximum of 60 subjects), divided equally (10 subjects) in each gestational age group. Based on the vulnerability of subjects at the time of study eligibility, subjects may be consented prior to meeting all inclusion/exclusion criteria. Subjects must go on to meet all inclusion/exclusion criteria prior to conducting study procedures, any subject who does not go on to meet all inclusion/exclusion criteria will be considered a screen failure and will be withdrawn from the study. Subjects will be enrolled until the target numbers of 10 completed subjects in each gestational age groups are met: Group 1, 22 0/7 – 24 6/7 weeks, Group 2, 25 0/7 – 31 6/7 weeks and Group 3, \geq 32 0/7 weeks is achieved.

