4.8. Criteria for Withdrawal/Discontinuation

A subject may withdraw from study participation at any time, for any reason. The Investigator may withdraw a subject at any time, for any reason. The reasons for withdrawal and discontinuation for any subject shall be recorded on an electronic Case Report Form (eCRF). These will be reported to the Sponsor. The EC should be notified per their notification of subject withdrawal policy.

Subjects who are enrolled but do not receive/undergo the study intervention may be replaced. Withdrawn or discontinued subjects who are enrolled, and who do not complete at 30 minutes of monitoring on each device, will not be considered complete and will be replaced. Subjects who withdraw or are withdrawn by a member of the study team prior to completion of all study procedures may have their completed data used as part of the study.

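### A device fault that ends a recording before 30 minutes, or is handled as a pause, is not scored in the non-inferiority test, and no visible sensitivity analysis keeps it

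*Combined protocol and SAP*

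**What the plan says.** Section 3.2.1 defines reliability as the "percentage of time in which the device gives FHR reading during the study monitoring period". Section 10.3.2 computes the success rate (SR) for each woman and device as samples with a fetal heart rate (FHR) value over all samples. A sample counts as a failure when "the device is turned on but has a value of 0".

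Two further rules in Section 10.3.2 decide what reaches that calculation. If either device "has less than 30 minutes of recording, the data from both devices will be eliminated from the primary endpoint analysis"; those data are not used in the test "but could be used for engineering development". Gaps that arise because the procedures were paused are taken out of the 30 minutes.

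The surrounding sections work as follows:

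- Section 4.3: "Subjects will be enrolled until the target numbers of 10 completed subjects in each gestational age groups are met".
- Section 4.8: withdrawn or discontinued women "who do not complete at 30 minutes of monitoring on each device, will not be considered complete and will be replaced". Women withdrawn "prior to completion of all study procedures may have their completed data used as part of the study", but Section 10 names no analysis that uses such data. Reasons for withdrawal go on the eCRF.
- Sections 8.5 and 10.3.3(b): device deficiencies, which include malfunctions, are documented and tabulated.
- Section 10.3.4: the only other analysis of the endpoint is an optional gestational-age subgroup analysis.
- Section 10.4: nothing is imputed.

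**The concern.** A monitor that loses signal while running is penalised. A monitor that stops running is not: the lost time is in neither the numerator nor the denominator, and the whole pair leaves the test. If the fault is instead treated as a pause and the session resumes, the recording can reach 30 minutes with the downtime removed. By either route a failure to deliver a reading goes unscored in an endpoint meant to measure how often the device delivers one.

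The test then describes completed recordings, with downtime removed, rather than the monitoring period. With about 30 pairs a few exclusions could decide the result, and the results are intended for regulatory submissions (Section 1).

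**Working it through.** **1. Can a fault enter the estimate?** There are three cases.

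- Signal lost, device on: the value is 0, so it is scored.
- Recording ends before 30 minutes: the pair is eliminated whatever the cause, so it is not scored.
- Fault handled as a pause: the gap is removed, so it is not scored. The visible text does not say whether a fault counts as a pause.

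**2. Is it recovered elsewhere?** Withdrawal reasons and deficiency tables record events, but nothing links them to the eliminated recordings or to the primary estimate. Sections 10.1 to 10.5 contain no sensitivity analysis.

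**3. How large could it be?** The plan has no figure to reproduce: Section 10.2 says the sample size is not powered, and no SD, expected SR or failure rate is given.

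From the documents: margin -10 percentage points, two-sided 95% CI (Section 10.1), 30 data sets (Section 10.2), 4 samples per second (Section 10.3.1).

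Assumed: a paired t interval; 30 completers with mean difference 0 and paired SD s = 5, 10 or 15; SR 90% while recording. A Lotus stop at minute 10 then has SR 90 × 10/30 = 30%, a difference of 30 - 90 = -60.

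With k such stops added to the 30 completers:

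- N = 30 + k and m = -60k/N
- SS = 29s² + 30m² + k(-60 - m)²
- lower limit = m - t(0.975, N-1) × √[SS / ((N-1)N)]

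Example, k = 3 and s = 10: m = -180/33 = -5.45. SS = 2900 + 892.6 + 8925.6 = 12,718.2. Standard error = √[12,718.2/(32 × 33)] = 3.470. With t = 2.037, the limit is -5.45 - 7.07 = -12.52.

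| Stops at minute 10 | SD 5 | SD 10 | SD 15 |
|---|---|---|---|
| None counted (plan) | -1.87 | -3.73 | -5.60 |
| 1 Lotus | -6.28 | -7.29 | -8.64 |
| 2 Lotus | -9.35 | -10.11 | -11.21 |
| 3 Lotus | -11.89 | -12.52 | -13.47 |
| 3 Corometrics | -0.98 | -1.61 | -2.56 |
| 3 on each device | -8.55 | -8.95 | -9.59 |

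If the three Lotus stops are not replaced (27 completers), the plan gives -1.98/-3.96/-5.93 and counting them gives -13.06/-13.70/-14.65.

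Timing matters. The number of Lotus stops needed to bring the limit to -10 or below, at SD 5/10/15, is 3/2/2 for minute 10, 4/4/3 for minute 15 and 8/7/5 for minute 20. For minute 25 it is not reached with 30 stops at SD 5, and takes 29 and 21 at SD 10 and 15.

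**The case against.** **Failures may be rare or absent.** This stands as a limit on size. Nothing in the documents suggests a rate, and one Lotus stop at minute 10 reverses nothing at any of the three SDs.

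**A restart may rescue the session.** This stands in part. The procedure steps are redacted, so a restart rule may exist unseen. The visible pause rule could let an interrupted session still reach 30 minutes, and the 5-minute session allowance in Section 5.1 does not cap this if the clock stops during a pause. But a rescued session has its downtime removed, so the fault still goes unscored.

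**Failures are already visible.** Partly true. Deficiencies are tabulated, withdrawal reasons are recorded and the analysed sample size is reported. A reader would see that something happened, but not which eliminated recording it caused, nor its effect on the estimate.

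**The endpoint is signal reliability with the device on, not uptime.** Section 10.3.2 can be read that way, while Section 3.2.1 refers to the monitoring period. This is a reason to keep the primary analysis and add to it, not to replace it.

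**The tempting stronger reading** is that the rule favours Lotus. The documents do not support that. The rule is symmetric, Corometrics failures are dropped too, and three Corometrics stops in the illustration would make the plan work against Lotus. Equal failure leaves the mean difference unbiased.

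**Conclusion.** The point holds in a limited form. Following Section 10.3.2 exactly can leave device-caused early stops, and faults handled as pauses, out of a test of reliability over the monitoring period, and no visible analysis puts them back. The bias runs toward the device with more such faults and is nil if there are none.

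Under the assumed inputs, two or three early Lotus stops could separate the plan's conclusion from one that counts them; one would not, and stops near minute 25 hardly matter. These figures show sensitivity and predict nothing about this study. A reader might infer that signal loss is being discarded or that the planned conclusion would be wrong. Neither follows: signal loss with the device on is scored, and no failure rate is given. This is a cheap improvement to the plan, not a defect in its primary analysis.

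**What to change.** Keep the complete-30-minute set as the primary analysis, with margin and sample size unchanged.

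1. **Governing sensitivity analysis.** Add to Section 10.3.2 an analysis of all women monitored on both devices that counts device-caused unrecorded time as no FHR, up to 30 minutes per device (30 × 60 × 4 = 7,200 samples). Include device-caused downtime inside a pause. Take the cause from an eCRF field completed at the time. Pairs shortened for other reasons stay excluded.
2. **Worst-case run for Lotus.** The study is open label (Section 4.1) and analysed by the sponsor's team (Section 10.3), so attribution of cause needs a check. Count every Lotus shortfall of any cause as no FHR, but only documented device-caused shortfalls for Corometrics. Pairs shortened only by another Corometrics cause stay excluded. Counting all shortfalls on both devices would not serve as a bound: with three device-caused Lotus stops and three unrelated Corometrics stops, it gives -8.55/-8.95/-9.59 and passes, while analysis 1 gives -11.89/-12.52/-13.47 and fails.
3. **Section 10.4.** State that this scoring applies to the sensitivity analyses only.
4. **Reporting.** List every eliminated recording, every device-caused pause, and every woman whose participation ended before the second device was started, by device and cause. The last group cannot enter a paired analysis, so state its number beside the result.
5. **Interpretation.** If analysis 1 does not support non-inferiority, report that beside the primary conclusion and limit the conclusion to completed recordings.

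The cost is one eCRF field, one table and two extra runs. The supporting result may be less favourable than the primary one.

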Eligibility Criteria:	
Inclusion criteria:
 
Subjects who meet all the following inclusion criteria may be enrolled:
 
1. Able and willing to provide written informed consent.2. Singleton pregnancy3. Aged 18+4. Greater than or equal to 22 0/7 weeks gestation5. Patient has none of the exclusion criteria.	
Exclusion criteria:
 
Subjects who meet any of the following exclusion criteria may not be enrolled:
 
1. Multiple pregnancy.2. Involvement in another clinical trial currently or previously in this pregnancy that, in the investigator's opinion, would affect the conduct of this study.3. Medical or obstetric problem that in investigator's opinion would make the patient incapable of taking part in the study.4. Inability to understand the consent information due to medical illness, diminished intellectual capacity, or insurmountable language barrier. 
[REDACTED]
 
[REDACTED]

Study Title: Maternal Fetal Device Performance Testing During Antepartum Singleton Monitoring

Study Number: SA-000072

Version Number: 2.0

Version Date: 23SEP2024

GE HealthCare

Sample Size and Sites:

This study is intended to be conducted at one United States site. Subjects will be divided into three groups based on gestational age groups.

Table 1: Target Enrollment Groups

Subject Gestational Age Groups	Target Enrollment
Group 1: 22 0/7 – 24 6/7 Weeks	10
Group 2: 25 0/7 – 31 6/7 Weeks	10
Group 3: ≥ 32 0/7 Weeks	10

[REDACTED] randomization schema will be provided by the sponsor within each gestational age group.

Sample Size and Site:

The sample size has not been derived from a statistically powered endpoint but has been determined based on a review of the literature, bench testing results and publicly available regulatory filings.

[REDACTED] The study is expected to last 4 months.

Study Duration:

[REDACTED] The study will be deemed completed following completion of data collection of the last enrolled subject.

Study Title: Maternal Fetal Device Performance Testing During Antepartum Singleton Monitoring

Study Number: SA-000072

Version Number: 2.0

Version Date: 23SEP2024

GE HealthCare

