1. BACKGROUND AND JUSTIFICATION

Maternal Fetal Monitoring devices assist the health care professional in acquiring, monitoring, and storing fetal and maternal physiologic data which supports the decision making for pregnant women and the overall fetal health status during pregnancy and delivery. These devices are often used during labor to monitor physiologic parameters including:

- Fetal heart rate (FHR)
- Maternal parameters such as maternal heart rate (MHR), blood pressure, temperature, and pulse oximetry and
- Uterine Activity (UA)

Maternal Fetal Monitoring devices are not treatment devices; their performance and indirect benefit is best measured by the accuracy of the physiologic data provided. Their performance is also measured by their ability to provide the relevant physiologic data, especially the FHR, which can be difficult to obtain.

Plotting of the FHR and uterine activity on the same graph is referred to as a cardiotocography (CTG). There are three types of FHR and uterine activity devices that are used to comprise the CTG:

- An internal fetal scalp electrode (FSE) is used to obtain FHR with an internal intrauterine pressure catheter (IUPC) used to measure contractions during labor.
- An external Doppler ultrasound (US) device is used to record the fetal heart rate and is used with an external tocodynamometer (TOCO) used to sense pressure during contractions.
- An external device to capture the fetal electrocardiogram (fECG) and uterine electromyography (EMG)

Of the three ways to measure FHR, a fetal scalp electrode is generally considered the gold standard for accuracy, but this invasive method requires ruptured membranes and a dilated cervix and is contraindicated with some maternal infections and fetal conditions. Doppler Ultrasound (US) is non-invasive and utilizes an external transducer placed on the maternal abdomen to detect fetal cardiac valve movements utilizing high frequency sound waves. US/Tocodynamometer (TOCO) are the most common type of CTG and the term CTG is sometimes used to refer specifically to that method of fetal-maternal monitoring. However, there are challenges with this method due high sensitivity of fetal and maternal movements causing signal void, thus the transducer must often be adjusted to correctly detect the FHR. The accuracy of FSE and US Doppler FHR measurements are not often the subject of publication, likely because the devices are well-established and considered the standard of care.^{1,2}

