4. STUDY DESIGN

4.1. Summary of Study Design

This is a pre-market, open label, prospective, randomized research study conducted at one site.

The study will be considered complete when subject enrollment and data collection requirements are met.

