5. STUDY PROCEDURES

5.1. Subject Preparation

Study staff will confirm that the subject is eligible and complies with applicable site requirements prior to starting study procedures.

After providing consent, the subject will be enrolled in the study.

Pregnant women of \geq 22 weeks gestation will undergo two 30 (+5 minute range) -minute monitoring sessions (60 minutes total).

Study Title: Maternal Fetal Device Performance Testing During Antepartum Singleton Monitoring

Study Number: SA-000072

Version Number: 2.0

Version Date: 23SEP2024

GE HealthCare

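### The primary comparison is not stated to be paired and has no term for device order, which can cost precision and, if order is unbalanced among analysed women, can bias the non-inferiority result in either direction

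*Combined protocol and SAP*

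**What the plan says.** **Design.** Section 5.1 states that women "will undergo two 30 (+5 minute range) -minute monitoring sessions (60 minutes total". Section 4.8 treats as incomplete, among withdrawn or discontinued subjects, those "who do not complete at 30 minutes of monitoring on each device, will not be considered complete and will be replaced". Section 4.1 describes the study thus: "This is a pre-market, open label, prospective, randomized research study conducted at one site". The Synopsis (Sample Size and Sites) adds that a "randomization schema will be provided by the sponsor within each gestational age group", with the words just before it blacked out. The Synopsis procedure steps are redacted, and Section 5.2 shows none.

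**Analysis.** Section 10.1: "The test will be performed using two-sided 95% CI of the difference in Mean SR", and then "If lower 95% CI of the difference is greater than -10%, non-inferiority will be concluded". Section 10.3.2 repeats this rule: "The difference in mean SR (Lotus – Corometrics 259cx) will be computed along with its two-sided 95% CI to test non-inferiority". Section 10.3.1 offers a t-test or a non-parametric method for continuous variables. Sections 10.1 to 10.4 mention no pairing, session, period, sequence or device order.

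**What can unbalance order.** Section 10.3.2 drops both recordings if either is shorter than 30 minutes. Section 4.8 replaces incomplete subjects, and Section 4.3 allows up to 60. None of these visible rules refers to device order.

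**Wording that fits poorly.** Section 10.3.2 opens by taking, for each subject, the time over which both devices record independently. Read alone, that could mean simultaneous recording.

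**The concern.** Two devices at 30 minutes each within a 60-minute total implies one after the other, so this is in effect a two-period crossover. Since every woman receives both devices, device order is the natural thing to randomise, although the visible text does not say so.

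SR measures how often the signal is present, and Section 1 says of Doppler that "there are challenges with this method due high sensitivity of fetal and maternal movements causing signal void, thus the transducer must often be adjusted". Movement and transducer position can differ between the first and second half-hour. If they change systematically, the change enters each woman's Lotus minus Corometrics difference with a sign set by which device came first. An analysis that ignores order leaves that change in the error and, when the two orders are unequally represented, in the estimate. This is the only confirmatory test, is meant for regulatory submissions, and rests on a sample size that Section 10.2 says was not derived from power.

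**Working it through.** **Inputs from the plan.** N = 30 data sets (Section 10.2), two-sided 95% CI and −10 point margin (Section 10.1). The plan gives no SD, expected SR, power or session effect, so it has no figure of its own to reproduce.

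**Assumptions.** 30 independent pairs; normal within-woman differences with SD 15 points (10 also tried); session effect p of 0, 5 or 10 SR points. The unadjusted analysis is read as a paired t interval, which the plan does not state. An unpaired interval would depend on the within-woman correlation, for which the plan gives nothing.

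**Model.** For woman i, d = δ + p if her order favours Lotus and d = δ − p if it favours Corometrics, plus error. Let n1 and n2 be the numbers in each order.

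- Bias of the plain mean: p × (n1 − n2)/30.
- Variance of d, ignoring order: SD² + p² × (1 − k²) × 30/29, where k = (n1 − n2)/30.
- Order-adjusted estimate: the average of the two sequence means. Its standard error is ½ × SD × √(1/n1 + 1/n2), on 28 df.

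**Balanced order, 15/15, SD 15.** Bias is 0.

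| p | Unadjusted half-width | Adjusted half-width |
|---|---|---|
| 0 | 2.045 × 15/√30 = 5.60 | 2.048 × 15/√30 = 5.61 |
| 5 | 2.045 × √(225 + 25.9)/√30 = 5.91 | 5.61 |
| 10 | 2.045 × √(225 + 103.4)/√30 = 6.77 | 5.61 |

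By simulation, the chance of passing at a true difference of 0 is 94%, 92.5% and 87.5% for p = 0, 5 and 10 unadjusted, and 94% adjusted. At a true difference of −10 points, the unadjusted false-pass rate is 2.0% for p = 5 and 0.9% for p = 10, both under the nominal 2.5%.

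**Unbalanced order, 18/12.** (18 − 12)/30 = 0.2, so the bias is 5 × 0.2 = 1 point or 10 × 0.2 = 2 points. False-pass rates at a true −10 points, over SD 10 and 15 and p = 5 and 10:

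- imbalance favouring Lotus: about 4–5% (at SD 15, 4.3% for p = 5 and 5.1% for p = 10);
- imbalance the other way: 0.01–0.8%;
- order-adjusted: about 2.5%.

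**How often such splits occur.** Under simple 1:1 randomisation of order, a split of 18/12 or worse has probability 36%, or 18% in Lotus's favour. A split of 20/10 or worse has probability 10%, or 5% in Lotus's favour; at exactly 20/10 favouring Lotus the false-pass rate is 7–17%. Averaged over all splits, the unadjusted false-pass rate is 2.5–2.6%.

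**Cost of adjusting when there is no session effect (SD 15).** The half-width goes from 5.60 to 5.61 at 15/15, 5.73 at 18/12 and 5.95 at 20/10.

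**The case against.** The design text that would settle this is redacted. The schema may randomise order in blocks within each gestational age group, which would keep it near balance before exclusions. The opening of Section 10.3.2 can also be read as concurrent recording. And the plan says only that movement and positioning cause signal loss, not that SR drifts from the first session to the second. All of this stands: sequential use is a strong inference, and the session effect is plausible but undocumented.

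A reader might infer that the omission inflates the false-pass rate. The documents do not support that. Nothing shows that order is unbalanced. With balanced order the unadjusted test is conservative; simple randomisation of order keeps the average error at nominal; and an imbalance can as easily count against Lotus. The 7–17% rates need a 20/10 split in one direction.

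A reader might also infer a large loss of power. At SD 15 and a 5-point effect with balanced order, the half-width rises by 0.3 points and power at a true difference of 0 falls by about 1.5 percentage points.

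What the objection does not remove is the omission itself. It lies in readable analysis text, and a hidden randomisation scheme would not supply a missing analysis term.

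**Conclusion.** The point holds in a limited form. The visible primary analysis states neither pairing nor an adjustment for device order, in a design that appears to be sequential within each woman. With order balanced among analysed women, the consequence is lost precision in a conservative direction: small for a 5-point session effect, more noticeable at 10 points. Bias arises only with unequal order counts, which dropped pairs and replacements can cause. At 18/12 it is 1 or 2 points, in either direction.

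Every magnitude is conditional on the assumed SD, session effect and paired interval. The conclusion also depends on the redacted schema randomising device order. If order is fixed, device and session are fully confounded and no analysis can separate them. This is a worthwhile, nearly free protection of the single confirmatory test, not evidence that the planned result would be wrong.

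**What to change.** In Section 10.3.2, before data are seen:

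1. Compute the difference and its two-sided 95% CI from within-woman Lotus minus Corometrics differences, adjusted for device order. Either average the two sequence-specific mean differences with pooled variance, or fit a mixed model with device and period as fixed effects and woman as a random effect. Section 4.5.2 lets a woman join more than one gestational age group. The pooled-variance form would treat her repeat records as independent, so the woman effect is preferable if this happens.
2. Keep the −10% rule.
3. Report mean SR by device and session descriptively. This should not be presented as isolating carry-over, which in a two-period design cannot be told apart from sequence differences or a device-by-period interaction.
4. State that device order is what is randomised, if so, and reconcile the opening sentence of Section 10.3.2 with the two sessions in Section 5.1.

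Replacement subjects should not be made to take the order of the woman they replace: in an open-label study that would reveal the allocation in advance.

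The cost is SAP wording, one model term and one degree of freedom, using an order variable that the trial should already hold. With no session effect, the half-width grows by 0.01 points at 15/15, about 0.1 at 18/12 and 0.35 at 20/10 (SD 15).
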